5.5. Benefit-to-Risk Rationale

Any potential risk presented by this clinical study has been minimized and adequate testing, safeguards, and safety monitoring have been incorporated into the clinical study to further minimize and mitigate the risks. Based on the review of all risks, residual risks, and risks resulting from risk mitigation, Argon has determined that the risks to participate are acceptably low. The devices will be used in accordance with their approved indications and standard of care for the subject population is being followed. The potential benefits outweigh the potential risks of using the Scorpion set and participating in this study.

6. DESIGN OF THE CLINICAL STUDY

6.1. Study Objective

The primary objective of this clinical study is to evaluate the safety and effectiveness of portal vein access sets during TIPS with the goal of creating the parenchymal tract for indicated interventional procedures. The study will collect safety and effectiveness data on the Scorpion set which will be compared to data collected on the Cook Transjugular Liver Access Set.

6.2. Study Hypothesis

No formal study hypothesis will be tested, but it is expected that the safety and effectiveness of the Scorpion set are similar to the Cook Transjugular Liver Access Set.

6.3. Study Design

This is a prospective, multicenter, randomized comparative post-market study in the United States (US). The study consists of a one-day intervention in subjects indicated to undergo a TIPS procedure with the aim of collecting real world safety and effectiveness data on the Scorpion set and comparator devices.

The Cook Transjugular Liver Access set was chosen as the comparator device because it is commonly used.

6.4. Study Endpoints

6.4.1. Primary Effectiveness Endpoint

The primary effectiveness endpoint is procedural success defined as creation of the parenchymal tract between the hepatic vein and an intrahepatic branch of the portal vein and confirmed by portogram (CO₂/contrast).

Failure to create the parenchymal tract between the hepatic vein and the portal vein with the randomized assignment will be considered a treatment failure. A minimum of 5 needle passes should be attempted before selecting the alternative set.

In the event of a treatment failure, the physician will follow their standard of care procedures and/or use another commercially available product. The patient should be followed in the study through hospital discharge for adverse event monitoring.

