3.2. Prior Investigations

The Rosch-Uchida and Colapinto sets manufactured by Cook Medical (Bloomington, Indiana, US) are two different needle sets currently available and most encountered. A recent systematic review of literature showed that the overall incidence of PVPC with the Cook sets was 3.6%.⁶ The procedure duration varies in literature due to protocol differences and imaging techniques used. David et al.⁷ reported a mean procedure duration of 86.2 minutes using ultrasound guidance. In a study evaluating time to portal vein access, mean time to portal venous access was statistically significant between conventional fluoroscopy at 46 minutes and intravascular US-guided TIPS at 31 minutes.⁸

In the paucity of studies available which focus on portal vein access in TIPS interventions, there are few that demonstrate significant differences between the number of needle passes. The data is incomplete because fewer than half of conventional TIPS cases in literature included a recording of the actual number of passes. The Scorpion devices allow for bi-directional positioning of the needle or stylet for precise placement during portal vein puncture.

In a retrospective study of 15 cases with Scorpion X (Needle model), technical success was achieved in 100% of cases with an average of 2.7 passes, and because of the bi-directional needle, no cases required adjustment to the curvature of the needle.⁹

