6.4.3. Secondary and Exploratory Endpoints

The secondary and exploratory endpoints of this clinical study are outlined in **Table 5**.

TABLE 5. OVERVIEW OF SECONDARY AND EXPLORATORY ENDPOINTS

Endpoint	Description / Definition
Secondary Endpoints	
Portal Vein Access (PVA) time	Time (in minutes) from initial needle throw to portal vein access as confirmed by portogram
Technical success	Creation of a shunt (stent bridging) between the portal and systemic veins
Number of needle passes	Count of needle throws between the hepatic and portal vein to create the parenchymal tract
Procedure duration	Interval (in minutes) from first jugular access for TIPS creation to removal of catheters from subject
Fluoroscopy time	Measured in minutes
Device-related complications	Incidence of complications related to the device as judged by the Principal Investigator
Exploratory Endpoints	

Change in MELD score	Change in score from Screening to Day 30
Change in Child-Pugh score	
Radiation dosage	Measured in air kerma (mGy)
Contrast volume used	Measured in mL
Length of Hospital Stay	Measured in days
Number of ICU days	Measured in days
Change in HPVG	Measured in mm Hg

MELD = Model for End-Stage Liver Disease; ICU = Intensive Care Unit; HPVG = Hepatic Venous Pressure

Gradient

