7.8. Blinding

This is an open-label study. Blinding is not utilized.

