8.3. TIPS Procedure (Day 0)

The TIPS procedure will be completed in a clinical setting with adequate angiographic equipment and institutional facilities, physiologic monitoring equipment, and support personnel.

Transjugular liver access will be obtained using either the Scorpion set or Cook set per randomization assignment and physician choice of model. The procedure will be performed in accordance with the Scorpion IFU or the Cook IFU. Refer to the current IFU included with the device for techniques and methods for pre-procedure preparation and directions for use. The specific model and treatment details (e.g., access site, access side, stent, etc.) will be determined by the physician based on the condition of the subject.

A minimum of 5 needle passes should be attempted with the initial device assigned through randomization before selecting the alternative manufacturer set. If an alternative manufacturer set is selected, the information will be recorded as part of the study records.

The following procedure data are to be collected and recorded in the subject's medical record or other applicable source documents which will be reported on the appropriate eCRF:

Jugular access site
Number of needle passes
Hepatic vein used for access
Access device used
Portal vein access site
Imaging used
Alternate access sites/techniques used
Sheath used
Stent used, dilated to what size
Pressure gradient measurements: pre- and post-delivery of stent
Presence of residual varices
Adverse events (during and post procedure)
Record Concomitant Medications (only rifaximin, lactulose, and medications which are an anticoagulant, antiplatelet, or diuretic will be recorded)

A portogram must be obtained to confirm creation of the parenchymal tract between the hepatic vein and an intrahepatic branch of the portal vein upon portal vein access and following stent deployment.

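### Procedural success has a floor of 5 passes but no common point at which it is judged, so operator persistence after pass 5 can move the rate; add a supportive analysis of access within 5 passes

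*Combined protocol and SAP*

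**What the plan says.** Procedural success (Section 6.4.1) is creation of the parenchymal tract, confirmed by portogram. On failure the section says: "Failure to create the parenchymal tract between the hepatic vein and the portal vein with the randomized assignment will be considered a treatment failure". It then gives the floor, "A minimum of 5 needle passes should be attempted before selecting the alternative set", which Section 8.3 repeats: "A minimum of 5 needle passes should be attempted with the initial device assigned through randomization before selecting the alternative manufacturer set". Both sentences use the verb *should*. Neither section, nor any other, gives a maximum number of passes, a time limit or another common point of assessment.

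Section 7.8 states: "This is an open-label study. Blinding is not utilized".

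Needle passes are a secondary endpoint, defined in Table 5 as "Count of needle throws between the hepatic and portal vein to create the parenchymal tract". The procedure data in Section 8.3 include "Number of needle passes", the access device used and any change to the other manufacturer's set. They do not say that passes are counted separately for each set.

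Success rates are assessed in the intent-to-treat set of Section 11.3.1, which holds all attempted procedures whether or not another device was needed. Device-specific outcomes use the set in Section 11.3.2, which holds only successes achieved without an alternative device.

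The only pass count in the documents is in Section 3.2, for 15 retrospective Scorpion X cases: "technical success was achieved in 100% of cases with an average of 2.7 passes". No figure is given for the Cook sets.

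**The concern.** Because the endpoint has a floor and no common assessment point, it combines two things: how readily a set reaches the portal vein, and how long the operator keeps trying with it. An unblinded person decides the second. Two sets with the same per-pass performance would show different success rates if operators persisted longer with one of them. If operators persisted for a long time with both, the two rates would approach 100% and a real difference would largely disappear.

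The other planned analyses do not close this gap. The Table 5 pass count runs up to tract creation, which leaves it undefined for failures. Outcomes analysed in the Section 11.3.2 set are conditional on success, so they too depend on persistence. No planned analysis scores all attempted cases at the same number of passes.

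No formal hypothesis is tested, so what is at stake is the descriptive success rates and the exploratory chi-square comparison (Section 11.1.2). These still matter: the arms are to be compared (Section 6.1), the data are meant for an initial CE Mark application (Section 3.3), and fewer passes is one of the benefits hoped for from the Scorpion set (Section 5.1).

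**Working it through.** The plan has no figure of its own to reproduce. The sample size is called empirical, and no effect size, power or significance level is stated.

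**Inputs.** Floor of 5 passes (Sections 6.4.1 and 8.3). Mean of 2.7 passes (Section 3.2; all 15 cases succeeded, so reading it as mean passes to access is reasonable). 30 subjects per arm (Section 6.6). Assumed: means of 4, 5 and 6; stopping at 8 or 10 passes; a two-sided 0.05 level.

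**Model.** With constant per-pass success p = 1/m, where m is the mean number of passes, access by pass k is 1 − (1 − 1/m)^k.

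**Identical sets, stopped at pass 5 in one arm and pass 8 in the other:**

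| Mean m | By pass 5 | By pass 8 | Spurious gap | Not accessed by pass 5, of 30 |
|---|---|---|---|---|
| 2.7 (cited) | 90.1% | 97.5% | 7.4 points | 3.0 |
| 4 (assumed) | 76.3% | 90.0% | 13.7 points | 7.1 |
| 5 (assumed) | 67.2% | 83.2% | 16.0 points | 9.8 |
| 6 (assumed) | 59.8% | 76.7% | 16.9 points | 12.1 |

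For example, at m = 4: 1 − 0.75^5 = 0.7627, 1 − 0.75^8 = 0.8999, difference 0.1372.

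**Patients who differ in difficulty.** Let p vary between patients as Beta(a, b), with b = (m − 1)(a − 1) so that the mean number of passes stays at m. The share not accessed by pass k is B(a, b + k)/B(a, b).

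- m = 2.7, a = 2: 8.90% at pass 5 and 4.42% at pass 8, a gap of 4.5 points.
- m = 2.7, a = 3: 9.84% and 4.26%, a gap of 5.6 points.
- m = 4, a = 2: 16.67% and 9.09%, a gap of 7.6 points.
- m = 4, a = 3: 19.58% and 10.00%, a gap of 9.6 points.

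The gaps shrink but do not vanish.

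**Effect on the planned test.** The rejection rate of the Pearson chi-square test at 30 versus 30 was enumerated exactly for identical sets, stopped at pass 5 versus pass 10.

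- Constant p: 27% at a mean of 2.7 and 55% at a mean of 4.
- With heterogeneity: 13–18% and 24–32%.
- Both arms scored at pass 5, constant p: about 5%, whatever operators do afterwards.

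**The opposite effect.** Take sets that truly differ, with means of 2.7 and 4 (assumed).

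- At pass 5: 90.1% versus 76.3%, a difference of 13.8 points.
- At pass 10: 0.99021 − 0.94369 = 0.04652, that is 99.0% versus 94.4%, a difference of 4.7 points.

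The chance that the chi-square test detects the difference is 30% at pass 5 and 6.5% at pass 10.

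**The case against.** The best defence is that success under ordinary operator discretion is a legitimate pragmatic measure in a real-world study that tests no hypothesis. It is also portogram-confirmed, whereas a pass count is operator-reported. That stands, and it is why the primary endpoint should stay as it is.

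A reader might go further than the text allows and infer that persistence determines the success rate, or that the comparison is biased toward one set. The documents do not support either. Persistence acts only on cases still open after pass 5, about 3 of 30 per arm at the cited mean. Nothing shows that it would differ by arm. Section 4.3 requires investigators to have experience with both sets and to be willing to use either. The same section requires sponsor certification for Scorpion only, and Section 13.2 allows sponsor specialists to assist. Those asymmetries make differential persistence possible but do not show that it occurs.

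Needle passes and portal vein access time are already secondary endpoints, so the study is not without efficiency measures. This helps less than it seems, because the pass count is undefined for failures and the set in Section 11.3.2 contains successes only.

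A 5-pass analysis has limits too. The floor is only a *should*, so an operator can change sets earlier. Table 5 does not say what counts as one throw. The protocol uses 5 as a switching floor, not a performance threshold. These points justify reporting early switches separately and showing the whole cumulative curve. They do not remove the value of a common scoring point.

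**Conclusion.** The point holds as a risk. The primary endpoint lacks a common assessment point, the operator is unblinded, and no planned analysis separates device performance from persistence after pass 5. For 5 versus 8 passes with identical sets, the possible spurious gap is 7.4 points at the only mean in the documents and 13.7 points at an assumed mean of 4. Under the heterogeneity models it falls to 4.5–5.6 and 7.6–9.6 points.

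These figures are illustrations. They rest on the assumed stopping points, on every unresolved case in an arm stopping at the same pass, and on a mean of 2.7 from 15 retrospective cases of one model. No Cook pass count is available, and neither the presence nor the direction of a bias can be read from the documents. A supportive analysis is worth adding because it costs little, not because the primary endpoint is invalid.

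**What to change.** Leave the primary endpoint and the switching rule unchanged. In Section 11, pre-specify a supportive effectiveness analysis:

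- **Outcome:** portogram-confirmed access with the assigned set within the first 5 passes.
- **Population:** the intent-to-treat set of Section 11.3.1, by randomised arm.
- **Early switches:** a change of set before pass 5 counts as not accessed, and such changes are reported separately by arm.
- **Display:** cumulative access with the assigned set by pass number, for each arm.

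In the eCRF instructions, ask sites to record the number of passes made with the assigned set, including in failures, and to count a pass in the same way in both arms.

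The cost is a paragraph of analysis text and a small eCRF clarification. The downsides are one extra effectiveness figure that will look lower than eventual success, and reliance on an operator-reported count. The analysis removes the influence of persistence after pass 5. It does not remove the influence of early switching, which is why that is shown separately.

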6.7. Study Duration

The study enrollment period is anticipated to take approximately 6 months. Enrolled subjects are followed for 30 days from the TIPS procedure requiring individual subject participation for approximately 1 month.

Upon completion of all enrolled subjects, study closure, including data analysis and preparation of the clinical study report, is estimated to take up to an additional 6 months.

Total study duration is expected to be approximately 13 months.

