8. STUDY PROCEDURES

8.1. Schedule of Assessments

The procedures and assessments for this study are outlined in the schedule of assessments (**Table 6**).

Study data will be collected at the following 5 time points: screening, TIPS procedure, hospital discharge, Day 7 follow up, and Day 30 follow up. Subjects will be exited from the study following completion of the Day 30 follow up visit or when they withdraw from the study. More detailed descriptions of the assessments are provided in subsequent sections.

Table 6. Schedule of Assessments

Procedure / Assessment	Screening ¹ (Day -90 to Day 0)	TIPS Procedure (Day 0)	Hospital Discharge	Day 7 ⁷ (± 1 day)	Day 30 (± 7 days)
Informed Consent	X				
Demographic Data	X				
Inclusion/Exclusion Criteria	X				
Medical History	X				
Physical Exam	X		X		X
Labs: CBC, CMP, PT, INR	X ²		X		X
MELD Score	X		X		X
Child-Pugh Score	X		X		X
Randomization		X ⁴			
TIPS procedure		X			
Duplex Ultrasound					X
CT or MRI	X ³				
Echocardiography	X ³				
Portogram		X ⁵			
AE Assessment		X ⁶	X	X	X
Concomitant Medications	X	X	X		X
Study Exit					X ⁸

¹ Assessments to be done prior to any study related procedure

² Within 30 days prior to the procedure

³ Preprocedural imaging via standard of care obtained within 90 days prior to the procedure

⁴ Randomization must be completed prior to TIPS procedure

⁵ At portal vein access and following stent deployment

⁶ Adverse Events will be assessed during and after the procedure

⁷ Phone call if subject has been discharged, in-person if subject is still in the hospital on Day 7

⁸ Study Exit may occur prior to Day 30 as Early Exit

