8.4. Hospital Discharge

At discharge from the hospital, usually between 1-7 days post TIPS procedure, subjects will be evaluated, and the following activities will be performed:

Physical examination, including at a minimum:

- Evaluation for hepatic encephalopathy
- Evaluation for presence of ascites

Blood draw, for clinical evaluation of the following labs:

- Complete Blood Count (CBC)
- Comprehensive Metabolic Panel (CMP)
- Prothrombin Time (PT)
- International Normalized Ratio (INR)

Determine MELD Score

Determine Child-Pugh Score

Adverse event assessment

Record Concomitant Medications (only rifaximin, lactulose, and medications which are an anticoagulant, antiplatelet, or diuretic will be recorded)

All data must be documented in the subject's medical record and reported on the appropriate eCRF.

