8.6. Day 30 (+/- 7 days) Follow Up

The 30 Day follow up assessment will be the final study visit and subjects will exit the study after completion of this follow up visit.

Thirty days (\pm 7 days) after the TIPS procedure, subjects will return to the clinic for a follow up visit during which the following activities will take place:

Physical examination, including at a minimum:

- Evaluation for hepatic encephalopathy
- Evaluation for presence of ascites

Blood draw, for clinical evaluation of the following labs:

- Complete Blood Count (CBC)
- Comprehensive Metabolic Panel (CMP)
- Prothrombin Time (PT)
- International Normalized Ratio (INR)

Determine MELD Score

Determine Child-Pugh Score

Duplex Ultrasound to assess hepatic venous patency, portal venous patency, and shunt status

Adverse event assessment

Record Concomitant Medications (only rifaximin, lactulose, and medications which are an anticoagulant, antiplatelet, or diuretic will be recorded)

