8.7. Study Completion

A subject will exit the study after completion of the Day 30 follow up assessments or an event that precludes further participation in the study.

The clinical study will be considered completed when all subjects have exited the study.

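### Section 6.4.1 follows treatment failures through hospital discharge, while the rest of the protocol follows subjects to Day 30; whether discharge is a minimum or an exit point for safety follow-up is not settled

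*Combined protocol and SAP*

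**What the plan says.** Section 6.4.1 defines a treatment failure as not creating the tract with the randomized set. It then gives these subjects a follow-up statement of their own: "The patient should be followed in the study through hospital discharge for adverse event monitoring". Section 8.4 places discharge early: "At discharge from the hospital, usually between 1-7 days post TIPS procedure, subjects will be evaluated".

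The general follow-up text runs to Day 30 and does not mention treatment failures:

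- 6.7: "Enrolled subjects are followed for 30 days from the TIPS procedure requiring individual subject participation for approximately 1 month".
- 8.1: "Subjects will be exited from the study following completion of the Day 30 follow up visit or when they withdraw from the study".
- 8.6: "The 30 Day follow up assessment will be the final study visit and subjects will exit the study after completion".

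Earlier exits are provided for only in general terms. Table 6 footnote 8 reads "Study Exit may occur prior to Day 30 as Early Exit", and 8.7 allows exit after "an event that precludes further participation in the study". Neither says whether treatment failure qualifies.

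The primary safety endpoint (synopsis and 6.4.2) is a composite of major complications associated with the device or procedure, with no time window in its definition. Treatment failures belong to the intent-to-treat set (11.3.1) and hence to the safety set (11.3.3).

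**The concern.** If sites read 6.4.1 as an exit point, the length of safety observation depends on the primary effectiveness result: successes are observed to Day 30 and failures only to discharge. Both groups count in the overall safety assessment.

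Events before discharge would still be captured, including puncture injuries recognised in hospital. At risk are related major complications that appear later. The endpoint covers the procedure as well as the device, and 10.4.1 lists hepatic encephalopathy, infection or sepsis, and liver failure among the events expected with TIPS. Section 11.4 does not say how an unobserved period after discharge is counted. If it is treated as event-free, the overall rate is understated. The arms would also be unequally observed if failure were more common in one of them.

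No hypothesis is tested, but the data are meant to support the initial CE mark application (3 and 3.3), and events that were never collected cannot be recovered at analysis.

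**Working it through.** The plan gives no figure to reproduce: the sample size is empirical (11.2), and no expected failure or complication rate is stated. The check is a comparison of the texts, followed by arithmetic on follow-up time.

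**1. What each reading implies.**

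- *Minimum.* 6.4.1 agrees with 6.7, 8.1 and 8.6. However, Table 6 already schedules adverse event assessment for every subject at discharge, Day 7 and Day 30, so the sentence adds nothing.
- *Exit point.* The sentence has content as a special rule for failures, and Table 6 footnote 8 leaves room for it. It then departs from 6.7 and 8.6, which contain no such exception.

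**2. Does another section decide it?** Section 10.5.1 has adverse event information collected for all subjects at every encounter, but does not say which encounters a failure has after discharge. It gives a start for reporting and no end. Section 8.8 does not list treatment failure among its withdrawal reasons, though that list is not exhaustive, and it asks for the Day 30 assessments at withdrawal if the subject is amenable. Both lean towards the minimum reading; neither states it.

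**3. Observation lost per failure under the exit reading.** Days lost = 30 − discharge day.

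- Discharge on Day 7: 30 − 7 = 23 days (23/30 = 77%).
- Discharge on Day 1: 30 − 1 = 29 days (29/30 = 97%).

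**4. Observation lost per arm.** With 30 subjects per arm (6.6) and an *assumed* number of failures f, person-days = (30 − f) × 30 + f × discharge day, out of 900.

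- f = 1: 871 to 877 (97%).
- f = 3: 813 to 831 (90 to 92%).
- f = 6: 726 to 762 (81 to 85%).

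**5. Missed events per arm, by assumption only.** Expected missed events = 30 × failure rate × risk of a related major complication after discharge, with unobserved time counted as event-free. Failure rates of 3 to 10% and risks of 2 to 10% are assumptions, not document figures.

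- Low end: 30 × 0.03 × 0.02 = 0.02 events; rate understated by 0.03 × 0.02 = 0.06 percentage points.
- High end: 30 × 0.10 × 0.10 = 0.30 events; rate understated by 0.10 × 0.10 = 1.0 percentage point.

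As a wider bound, section 3.2 reports technical success in all 15 cases of a Scorpion X series. The exact 95% upper limit for 0/15 failures is 1 − 0.025^(1/15) = 21.8%, or 30 × 0.218 = 6.5 failures. At the same risks this gives 0.13 to 0.65 missed events. That series may not use the 6.4.1 definition and says nothing about the Cook sets.

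**6. What would cost one event per arm?** Failure rate × risk must reach 1/30 = 3.3%. That needs a post-discharge risk of 0.033/0.10 = 33% at 10% failures, or 0.033/0.218 = 15% at 21.8%.

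The 3.6% incidence of puncture-related complications with the Cook sets (3.2) cannot supply the risk: it is narrower than the endpoint and is not split at discharge.

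**The case against.** The strongest reply is that 6.4.1 never uses the language of exit. It says only that failures should be followed through discharge. Failures are enrolled subjects, so 6.7 covers them on its face, and 10.5.1 and 8.8 point the same way. This stands as the better reading of the text, but sites should not have to infer it from a sentence that, so read, has no function.

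A second reply is that the collection period is already bounded in practice: reporting starts at the procedure (10.5.1), and the final visit is Day 30. That is true for subjects on the schedule. It does not help if it is unclear whether failures remain on the schedule.

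A third is that 10.2 classes complications of concomitant treatments not imposed by the protocol as not related. Some late events after completion with another product might therefore fall outside the endpoint. This is arguable, and it would lower the risks assumed above.

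Two stronger readings are tempting. A reader might infer that the protocol flatly contradicts itself, or that failures do leave at discharge. The documents do not support that, because the minimum reading is coherent. A reader might also infer that the comparison between arms is biased, or biased towards one device. That would require failure rates, or the risk or timing of events after discharge in failures, to differ between arms, and the documents give no such figures.

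**Conclusion.** The point holds as an unresolved ambiguity in safety follow-up, and it is worth correcting because the correction is cheap. If discharge is only a minimum, the effect is zero. If it is applied as an exit point, each failure discharged on Day 1 to 7 loses 77 to 97% of the 30-day observation period while remaining in the safety set.

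The resulting error in the primary safety rate cannot be derived from the documents. On the assumed ranges it is below one event per arm, and this rests on the assumed failure rates and post-discharge risks and on counting unobserved time as event-free. No size is claimed for any difference between arms. The device-specific post-operation safety analysis is unaffected, because 11.3.2 and 11.3.3 already restrict it to procedures completed with the study device alone.

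**What to change.** Reconcile 6.4.1 with 6.7, 8.1 with Table 6, and 8.6 so that adverse event data collection has the same length for every treated subject, whatever the procedural result. The existing Day 7 and Day 30 contacts suffice; Table 6 already provides for Day 7 as "Phone call if subject has been discharged, in-person if subject is still in the hospital on Day 7". This concerns data collection only, not the care given after a failed attempt.

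State the same window, from the start of the procedure through the Day 30 visit, for the primary safety endpoint in the synopsis and in 6.4.2. In the report, give by arm the number of treatment failures without Day 30 safety data.

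The cost is a short amendment with IRB approval (12.6.1), one added line in the report tables, and Day 7 and Day 30 adverse event contact for a few additional subjects: about 1 to 3 per arm at the assumed 3 to 10% failure rate (30 × 0.03 = 0.9; 30 × 0.10 = 3).
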